Various levels of acupuncture training have been taught to several hundred military physicians. A barrier to more widespread implementation has been lack of scientifically rigorous clinical trials to prove its worth in spite of the wide variety of anecdotal reports purporting its value in treating migraine. This trial will establish the efficacy acupuncture for acute migraine so that military beneficiaries can use less mind-altering medications. Additionally, many patients who have experienced traumatic brain injury develop chronic migraine that is refractory to medication, and acupuncture could be an important adjunct to this malady. Finally, management of medication side effects (i.e. chest pain in patients who take triptans) adds to costs that could be averted if acupuncture is effective. Proof that acupuncture is an effective treatment for acute migraine in military beneficiaries could result in fewer lost duty days, decreased medication use, and improved quality of life.

3.5. Background and Review of Literature:

Migraine is a recurring disorder characterized by attacks of severe headache generally associated with nausea, vomiting, and other neurologic symptoms. Duration is usually more than 4 hours and may last up to 72 hours with fluctuating intensity.¹ Migraine is commonly characterized as either episodic or chronic, depending on the frequency of attacks. Episodic migraine is more common, affecting up to 12% of the general population.² The direct medical costs of migraine headaches are approximately \$1 billion per year in the U.S.,³ with a national annual indirect burden of migraine estimated at \$12 billion (mostly attributed to absenteeism).³

Management of migraine focuses both on the treatment of acute attacks and the prevention of such attacks.^{4,5} The goals of migraine preventive therapy are to reduce attack frequency, severity, and duration; improve functional status/reduce disability; and improve response to acute treatments. The goal of acute treatment is typically to quickly eliminate or reduce the severity of migraine headache pain and associated symptoms. People who experience frequent migraine episodes often overuse

symptomatic medications. There are many “rescue medications” to choose from for the acute treatment of migraine, but side effects from pharmacologic approaches to migraine treatment can be considerable and often limit treatment options.

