- Review past medical history in Armed Forces Health Longitudinal Technology Application (AHLTA) to verify the inclusion/exclusion criteria including previous encounter, vital signs review, medication list, co-morbidities, demographics, problems list, and note any prior acupuncture received. (research only)
- Record: Date of birth, age, gender, race, ethnicity, last 4 of social security number, name of standard of care rescue medications (over-the-counter and prescription), current email address (to be used for scheduling only), height (in

inches), weight (in pounds), history of traumatic brain injury, concussion, or any mild to severe head trauma, medication use, history of acupuncture. (research only)

- We will ask what the subjects expectations are regarding acupuncture's effectiveness for migraine. (research only)
- We will instruct subjects not to take their over-the-counter and prescription headache medications until after their visit with the research staff. (Standard care)
- We will instruct subjects to bring their over-the-counter and prescription headache medications with them to each visit if their symptoms do not resolve from the acupuncture treatment. (research only)
- Patient will be instructed to contact the Research Coordinator, as soon as possible, after onset of migraine symptoms (including prodromal symptoms) to schedule an emergent visit with the research staff. (research only)
- Patient will be given a contact card with the names and phone numbers of the research staff to contact when they have a migraine episode.

Migraine Episode:

- Self-reported headache pain severity (0=no headache, 1=mild, 2=moderate, 3=severe) (Standard care)
- Record type and amount of rescue medications (over-the-counter and prescription) use in the past 7 days. (research only)
- Acupuncture treatments will be subject dependent, and points could include the N point (on scalp); various auricular points to include Shen Men, Point Zero, thalamus and Omega-2; body points to include Liver 2, Liver 3, Gall Bladder 20, bladder 10; and surface release over tense areas in the neck or shoulders. (Standard care)
- Researchers will document the points used. (Standard care)
*If after 20-30 minutes these patients have not had resolution of their headache, they may take their standard of care rescue medication. (research only)
- The subject will sit for 20-30 minutes post-acupuncture(research only), and then the needles will be removed and the subject will be asked:

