 - Self-reported headache pain severity (0=no headache, 1=mild, 2=moderate, 3=severe) (research only)
- Subject is allowed to leave and will be informed of the following telephone follow ups:
- 2 Hours post acupuncture:
 - Self-reported headache pain severity (0=no headache, 1=mild, 2=moderate, 3=severe) (research only)
- 4 Hours post acupuncture:
 - Self-reported headache pain severity (0=no headache, 1=mild, 2=moderate, 3=severe) (research only)
- 24 Hours post acupuncture:
 - Self-reported headache pain severity (0=no headache, 1=mild, 2=moderate, 3=severe)
 - Would you use acupuncture for future pain management? (Yes or no)
 - Would you prefer acupuncture or your rescue meds (both over-the-counter and prescription) for future episodes?
 - Record type and amount of rescue medications (over-the-counter and prescription) used since acupuncture. (research only)

Patients with missed phone calls will not be withdrawn from the study. If there is a missed call, we will mark as 'missed', including the reason and continue with the next phone call.

The Research Coordinator will record the name of the AI performing the acupuncture and also the placement of the acupuncture needles for each migraine episode.

Placement of Acupuncture:

[figure not shown]
Acupuncture treatments will be subject dependent, and points could include the N point (on scalp) (Figure 1); various auricular points to include Shen Men(Figure 2), Point Zero(Figure 3), thalamus(Figure 4) and Omega-2(Figure 5); body points to include Liver 2(Figure 6), Liver 3(Figure 6), Gall Bladder 20(Figure 7), bladder 10(Figure 7); and surface release over tense areas in the neck or shoulders. We will utilize the Seirin J-Type Acupuncture needles (Figure 98). Intermittent placement checks by the medical acupuncturist will be performed.

This study will follow all FDA requirements for the safe use of these devices.

Only the investigators listed on this study will perform the insertion of the acupuncture needles. All investigators are trained in this acupuncture technique and credentialed by the Credentials committees.

The Food and Drug Administration (FDA) regulates acupuncture needles as a class II medical device, because they are intended for use in the cure, mitigation, treatment, or prevention of disease in man or are intended to affect the structure or function of the body of man. The FDA regulates the acupuncture needles (see 21 CFR 880.5580), but not the practice of acupuncture itself.

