4.9.4. Injury Compensation: N/A

4.9.5. Data Safety Monitoring:

The principal investigator will be responsible for the protocol safety monitoring. The PI will make study documents (e.g., consent forms, data pulls) and pertinent hospital or clinical records readily available for inspection by the local IRB and oversight staff for confirmation of the study data.

5.0. Alternatives:

Acupuncture for migraine is done in the Family Medicine Residency as part of standard of care. Subjects may choose to get this type of acupuncture without participating in this study.

6.0. Data Analysis:

6.1. Outcome Measures:

Primary outcome: Reduction of migraine headache pain from mild, moderate or severe to pain free, 20-30 minutes, 2 hours, 4 hours and 24 hours post treatment. Secondary outcomes: patient global assessment of preference for trying acupuncture vs rescue medications; overall satisfaction and perceived effectiveness of the treatment; reduction of symptoms other than migraine headache pain; and use of rescue medication within 12 hours of the initial treatment (irrespective of which study treatment received). These standardized outcome measures are commonly used in comparative effective trials of migraine rescue medications. Researchers will document the points used, and data will be aggregated to determine overall effectiveness. Sub-group analysis by points will be performed to determine if there is more usefulness in 1 point or combination of points.

6.2. Sample size estimation/power analysis:

We will treat 30 subjects. We will administer up to 6 acupuncture treatments for up to 6 different migraine episodes per subject over the course of 3 months. We will not formally test a hypothesis. Rather, we will determine the proportion of migraines that resolve (as assessed by headache severity) 20-30 minutes, 2 hours, 4 hours, and 24 hours after the start of an acupuncture treatment. These data will be used to inform power calculations for future studies.

6.3. Statistical Analysis:

We will use descriptive statistics to characterize the clinical response of subjects after acupuncture treatments.

6.4 Number of Subjects:

Number of subjects planned for MOFMC	Enrolled in Study	60	to result in	30	completing the study.
--------------------------------------	-------------------	----	--------------	----	-----------------------

TOTAL NUMBER OF SUBJECTS (nation-wide/study-wide): 60

7. **Duration of Study:** Approximate duration of the study: 2 years

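### Three secondary outcomes in section 6.1 have no direct question at any listed contact, and the 12-hour rescue outcome has no recorded intake time behind it

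*Combined protocol and SAP*

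**What the plan says.** Section 6.1 (Outcome Measures) gives preference for acupuncture or rescue medication as a secondary outcome, followed by "overall satisfaction and perceived effectiveness of the treatment; reduction of symptoms other than migraine headache pain; and use of rescue medication within 12 hours". Counting satisfaction and perceived effectiveness separately, that makes five secondary outcomes.

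Section 3.6 (Research Design and Methods) lists what is asked, and when:

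- Screening: what the subject expects of acupuncture's effectiveness.
- Before each treatment: headache severity on a 0 to 3 scale, and "Record type and amount of rescue medications (over-the-counter and prescription) use in the past 7 days".
- At 20-30 minutes, 2 hours and 4 hours: headache severity only.
- At 24 hours: headache severity; a binary question, "Would you use acupuncture for future pain management"; a separate question on preference, "Would you prefer acupuncture or your rescue meds (both over-the-counter and prescription) for future episodes"; and a medication record, "Record type and amount of rescue medications (over-the-counter and prescription) used since acupuncture".

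On rescue, 3.6 states: "If after 20-30 minutes these patients have not had resolution of their headache, they may take their standard of care rescue medication". A missed call is marked as missed and the subject goes on to the next one.

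Three other places bear on the point. Section 3.5 describes migraine as "attacks of severe headache generally associated with nausea, vomiting, and other neurologic symptoms" and adds: "The goal of acute treatment is typically to quickly eliminate or reduce the severity of migraine headache pain and associated symptoms". Item 4 of the Protocol Summary makes satisfaction an aim. Section 3.6.1 promises patient-centred outcomes and receptivity without naming an item or a time. It also has a sentence on analgesic doses that can be read as covering the pre-treatment point and all four later times. The table in 3.6.5 counts the questions.

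**The concern.** Each outcome in 6.1 needs a question that produces it. A reduction in other symptoms needs a record before treatment and another after it. Perceived effectiveness needs a question after treatment; an expectation given at screening is a different quantity. Use within 12 hours needs either a contact near 12 hours or a time of intake.

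If staff follow the listed contacts and nothing more, the symptom outcome and perceived effectiveness end with no data. Satisfaction rests on questions that the plan never assigns to it, one of which already serves as the preference outcome. The 12-hour rescue proportion can only be bounded. Symptoms during an attack cannot be reliably reconstructed afterwards, so the loss could not be repaired at the analysis stage. The study is meant to prepare a comparison with rescue medication, and 6.1 itself presents these measures as customary in such trials.

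**Working it through.** **Step 1. Reproduce the plan's counts.** Inputs: the contact list in 3.6, the maximum of six episodes per subject (3.6 and 6.2), and the totals in 3.6.5. Formula: questions per episode × 6.

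| Question | Per episode, from 3.6 | × 6 | Total in 3.6.5 |
|---|---|---|---|
| Pain severity | 5 (before, 20-30 min, 2 h, 4 h, 24 h) | 30 | 30 |
| Future use | 1 | 6 | 6 |
| Preference | 1 | 6 | 6 |
| Rescue medication | 2 (past 7 days; since acupuncture) | 12 | 12 |
| Sum | 9 | 54 | 54 |

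The table's title says per migraine, but the figures fit only as totals per subject over six episodes (its acupuncture row is also 6), and I read it that way. On that reading, list and table agree in every patient-question row.

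**Step 2. Match outcomes to questions.**

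| Outcome in 6.1 | Listed questions that produce it |
|---|---|
| Preference | 1 of 9, at 24 h |
| Satisfaction | 0 of 9 directly; future use and preference are possible proxies, not declared as such |
| Perceived effectiveness | 0 of 9; the only effectiveness question is expectation, at screening |
| Symptoms other than headache pain | 0 of 9, before or after treatment |
| Rescue use within 12 h | 1 of 9, at 24 h, giving type and amount but not time |

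**Step 3. The 12-hour window under 3.6 and 3.6.5.** The last two contacts are 24 − 4 = 20 hours apart, and 4 < 12 < 24. Rescue is permitted from 20-30 minutes, so first use can fall on either side of 12 hours. Among episodes with a completed 24-hour call, no use by 24 h means no use by 12 h. Any use by 24 h leaves the 12-hour answer open.

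Let f be the share of episodes with any rescue use by 24 h. The 12-hour proportion then lies between 0 and f. The documents give no value for f, so I assume 0.20, 0.40 and 0.60. With all 24-hour calls completed and the maximum of 30 × 6 = 180 episodes, the bounds are 0 to 36, 0 to 72 and 0 to 108 episodes.

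**Step 4. The same window if 3.6.1 means doses at all five time points.** Use reported by 4 h is then a certain yes at 12 h. Let g be the share of users who report use by 4 h (assumed 0.5 or 0.8). The bounds become g × f to f.

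| f (assumed) | Under 3.6 and 3.6.5 | 3.6.1, g = 0.5 | 3.6.1, g = 0.8 |
|---|---|---|---|
| 0.20 | 0 to 0.20 | 0.10 to 0.20 | 0.16 to 0.20 |
| 0.40 | 0 to 0.40 | 0.20 to 0.40 | 0.32 to 0.40 |
| 0.60 | 0 to 0.60 | 0.30 to 0.60 | 0.48 to 0.60 |

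Only first use between 4 h and 24 h remains undetermined.

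**Step 5. Does 3.6.1 fit the rest of the plan?** Doses at five time points would mean 5 × 6 = 30 questions per subject. Doses before treatment only would mean 1 × 6 = 6. The contact list and the table have 2 × 6 = 12, so neither reading agrees. On the pre-treatment-only reading, post-treatment use still rests on the 24-hour record and Step 3 applies unchanged.

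**The case against.** The strongest objection concerns the rescue outcome. A reader might infer that 12-hour use is lost for every episode with rescue use, and for exactly those episodes. The documents do not support this. On the five-time-point reading of 3.6.1, use reported by 4 hours settles the answer. And 3.6 allows missed calls, so an episode with no rescue use but no completed 24-hour call may also be unclassifiable. What stands is that the 24-hour record has no intake time, that 3.6.1 conflicts with 3.6 and 3.6.5, and that first use between 4 and 24 hours is open on every reading.

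A second objection is that 3.6.1 does promise patient-centred outcomes. It does, but without an item, scale or time, so it states an intention and does not fill the gap.

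Third, the case forms may contain the missing questions. A reader might infer that these data will certainly not exist; that goes too far, because the forms are not in the documents and some pages were removed. The table in 3.6.5 is not a full inventory either: it omits the expectation question at screening. The agreement between list and table is therefore supporting evidence, and the claim is that no question is listed.

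Finally, the study is exploratory and descriptive, and section 6.2 plans no hypothesis test. That limits the consequences, but a descriptive outcome still needs data.

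**Conclusion.** The point holds. Of the five secondary outcomes in 6.1, one (preference) is fully supported by the listed contacts. Two (other symptoms, perceived effectiveness) have no listed question, and one (satisfaction) has only undeclared proxies. The fifth, rescue use within 12 hours, can be determined only in part: for users it is open under 3.6 and 3.6.5, and for first use between 4 and 24 hours it is open even under the wider reading of 3.6.1.

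This rests on taking the contact list in 3.6 as what staff will ask, and on reading 3.6.5 as totals over six episodes. The numerical bounds also rest on the assumed f and g and on completed 24-hour calls. Confidence is high that no question is listed; whether an unseen form holds one cannot be judged.

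The effect is confined to descriptive secondary outcomes. The primary outcome, the sample size and the headache-free proportions intended for later power calculations are untouched, and any rescue use over 24 hours can still be reported. It should be corrected, but it does not threaten the main aim.

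**What to change.** Preferred change, using contacts already scheduled:

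- Add a short yes/no checklist of associated symptoms (for example the nausea and vomiting named in 3.5) before treatment and at one or more follow-up contacts.
- At the 24-hour call add one satisfaction rating, one rating of perceived effectiveness, and the clock time of first rescue intake.
- If future use or preference is meant to stand for satisfaction, say so in 6.1.
- Clarify the sentence on analgesic doses in 3.6.1 and reconcile it with 3.6 and 3.6.5.

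With the checklist at one follow-up, this adds 2 + 1 + 1 + 1 = 5 short items, taking an episode from 9 to 14 questions. The cost is slightly longer calls plus wording in the protocol and forms; no visit, staff or procedure is added.

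Alternatively, delete from 6.1 whatever will not be collected (for satisfaction, also from item 4 of the Protocol Summary) and restate rescue use over 24 hours. That costs only wording but gives up those outcomes. The dose sentence in 3.6.1 needs reconciling either way.

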This will be an exploratory observational trial of rescue acupuncture for the treatment of acute migraine in military beneficiaries to gain information to inform the power analysis of a larger, more definitive trial. We do not seek to definitively answer the question of whether this acupuncture protocol is effective; rather, we seek to estimate the proportion of migraine episodes that result in headache-free status 20-30 minutes, 2 hours, 4 hours, and 24 hours after an acupuncture treatment. Acupuncture treatments will be subject dependent, and points could include the N point (on scalp); various auricular points to include Shen Men, Point Zero, thalamus and Omega-2; body points to include Liver 2, Liver 3, Gall Bladder 20, bladder 10; and surface release over tense areas in the neck or shoulders. Researchers will document the points used, and data will be aggregated to determine overall effectiveness. Sub-group analysis by points will be performed to determine if there is more usefulness in 1 point or combination of points. These estimates will inform statistical power calculations for a future randomized controlled trial (RCT) that directly compares the effectiveness of Rescue Acupuncture with medical management of acute migraine with rescue medication. We will also assess the feasibility of this study protocol as well as patient receptivity and satisfaction.

5. Subjects:

Male and female DoD beneficiaries ages 18 years or older will be recruited at the Mike O’Callaghan Federal Medical Center (MOFMC). No special populations (e.g., pregnant women, children, military basic trainees, prisoners, detainees) will be recruited.

6. Inclusion/exclusion criteria:

Inclusion:

- Male and female DoD beneficiaries, age 18 years or older, who have been previously prescribed rescue medication to treat their acute migraine episodes.

Exclusion:

- Pregnant
- Absence of ear
- Active cellulitis of ear
- Ear anatomy precluding identification of acupuncture landmarks
- Use of Hearing Aids that preclude the insertion of needles

- Use of anticoagulants
- Unable to drive during rapid onset of migraine or inability to find someone to drive you

7. Number of Subjects: TOTAL NUMBER OF SUBJECTS (nation-wide/study-wide): 60

8. Use of an Investigational New Drug: N/A

9. Use of an Investigational Device: Seirin J-Type Acupuncture needles and Sedatelec ASP Original Gold Acupuncture needles, 510(k) exempt as Class II device under 21 CFR 880.5580

10. Use of a Placebo: N/A

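### The sub-group analysis by acupuncture point is meant to establish which point is more useful, but points are not allocated and only descriptive statistics are planned

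*Combined protocol and SAP*

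**What the plan says.** The sub-group sentence, "Sub-group analysis by points will be performed to determine if there is more usefulness in 1 point or combination of points", appears three times: in the Protocol Summary (section 4, Brief Summary), in section 3.6.1 and in section 6.1.

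Point choice is described in the same sections and in section 3.6: "Acupuncture treatments will be subject dependent, and points could include the N point (on scalp"), followed by a list that brings the named options to ten. No selection rule or allocation is given. The only cue is for one option, "surface release over tense areas in the neck or shoulders", which depends on a presenting feature.

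Section 6.2 plans 30 treated subjects with up to 6 episodes each, states that no hypothesis will be formally tested, and ties later power calculations to the overall proportion of migraines that resolve. Section 6.3 is a single sentence planning descriptive statistics. It mentions no interval, clustering, adjustment or minimum count.

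Baseline severity is recorded at each episode, and "The Research Coordinator will record the name of the AI performing the acupuncture". Neither is given a role in the comparison of points. On timing, section 3.6 says: "If after 20-30 minutes these patients have not had resolution of their headache, they may take their standard of care rescue medication".

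**The concern.** The sub-group sentence sets a comparative aim, and the design and analysis cannot meet it. If practitioners choose points according to severity, neck tension, past response or their own habit, the pain-free rate for a point partly reflects who received it. That bias does not shrink as episodes accumulate. Separately, when ten options are compared on few episodes, one of them will come out on top by chance.

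At stake is one conclusion: a report, faithful to the plan, could name a more useful point or combination when there is none. The overall pain-free proportion pools all episodes whatever points were used, so it is not affected.

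**Working it through.** **No figure to reproduce.** The plan states no response rate, precision target or sub-group size for this analysis. The documents supply: 30 subjects, up to 6 episodes each (maximum 30 × 6 = 180), ten named options and four time points. The rest is assumed: 40% of episodes pain-free; each option used in 40, 60 or 80% of episodes; 60 episodes (two per subject) as a low case; and an intraclass correlation (ICC) of 0.3 where clustering is shown.

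**Chance.** All ten options are equally effective and are used independently by episode. Simulated results for 40/60/80% use:

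| Episodes | Mean best-worst gap (points) | Runs with gap of 10 points or more | Mean lead over runner-up (points) |
|---|---|---|---|
| 60 | 24 / 16 / 10 | 99 / 94 / 45% | 4.4 / 2.9 / 1.7 |
| 180 | 14 / 9 / 6 | 86 / 35 / 0.5% | 2.5 / 1.6 / 1.0 |

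Hand check: a point used in a fraction u of N episodes has a rate that varies around the overall rate with standard deviation of about √[0.24(1 − u)/(uN)]. The expected range of ten standard normal values is about 3.08.
- N = 60, u = 0.4: √(0.24 × 0.6/24) = 0.077; × 3.08 = 0.24.
- N = 180, u = 0.8: √(0.24 × 0.2/144) = 0.018; × 3.08 = 0.056.

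Both agree with the table. If each subject keeps the same points throughout and the ICC is 0.3, the mean gap over 60 to 180 episodes is 9 to 28 points and the mean lead 1.6 to 5.2.

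**Selection.** Take a point with no effect, and let half of attacks be severe.
- Used in 70% of severe and 30% of other attacks, with resolution rates of 20% and 50%. Used: 0.7 × 0.20 + 0.3 × 0.50 = 0.29. Not used: 0.3 × 0.20 + 0.7 × 0.50 = 0.41. Spurious difference: −12 points.
- Used in 60% and 40%, with resolution rates of 35% and 45%. Used: 0.6 × 0.35 + 0.4 × 0.45 = 0.39. Not used: 0.4 × 0.35 + 0.6 × 0.45 = 0.41. Spurious difference: −2 points.

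The signs reverse if the point is favoured in milder attacks.

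**Intervals for a single point.** With 30 subjects × 6 episodes and ICC 0.3, a simple 95% interval covers the true rate in 76-87% of runs; a bootstrap that resamples subjects covers it in 93-94%. The bootstrap needs enough subjects. If 30 episodes come from 5 subjects, coverage is about 85-87%; with 10 to 15 subjects it is about 91-93%. A threshold on episodes alone is therefore not enough.

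**The case against.** The best defence is that this is an openly exploratory, observational study. The Protocol Summary says "We do not seek to definitively answer the question of whether this acupuncture protocol is effective", section 6.2 rules out a formal test, and section 6.3 limits the whole analysis to description. Section 6.2 also uses the verb *determine* for a plain estimate of a proportion, so in the sub-group sentence it may mean no more than *describe*. Individualised points are the practice under observation, and the points used are recorded.

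Much of this stands. No test or multiplicity correction is called for, and the lack of a point-selection rule is not a design fault in itself. But the disclaimer concerns whether the protocol as a whole works, and asking whether one point is *more* useful remains a comparison. Nothing in the documents withdraws it.

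Three stronger readings are tempting and unsupported:
- **That point-level results will drive the power calculation of the later trial.** The Protocol Summary's sentence about estimates informing that calculation directly follows the sub-group sentence. Section 6.2, however, ties the calculation to the overall proportions, so no change is needed there.
- **That severity actually drives point choice here.** No passage shows this. Surface release is the only option linked to a finding, and the −2 and −12 point examples are constructed.
- **That a large spurious gap is bound to appear.** At 180 unclustered episodes with 80% use, a gap of 10 points or more occurs in about 0.5% of runs. The best-worst gap is also the most striking summary; the leader's margin over the runner-up is small.

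**Conclusion.** The concern holds in a limited form. As planned, the by-point comparison cannot support a conclusion that one point or combination is more useful, because selection and chance can each produce differences of a size that a reader might take for an effect. Under the stated assumptions the mean chance gap between best and worst is 10-24 points at 60 episodes and 6-14 at 180, wider if points are fixed within subjects, with a leader's margin of about 1-4 points. These figures rest on an assumed response rate, assumed point use and, where clustered, an assumed ICC. The argument about selection needs none of them. The consequence stops at the sub-group conclusion, so this is a minor to moderate point that is worth correcting because the correction is cheap.

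**What to change.** 1. In the Protocol Summary (section 4), section 3.6.1 and section 6.1, replace the sub-group sentence with: *Outcomes by point will be described for hypothesis generation only; because points are not randomly allocated, no conclusion about relative usefulness of points or combinations will be drawn.*

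2. In section 6.3 add: *For each point, the numbers of episodes and of subjects and the pain-free proportion at 20-30 minutes (before rescue medication is allowed) will be reported. A 95% confidence interval that allows for repeated episodes within subject (bootstrap resampling subjects) will be given only for points used in at least 30 episodes from at least 15 subjects; other points, and any split by baseline severity, will be shown as counts only.*

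**Cost.** One sentence replaced in three places and two added; no new data, visits or subjects. The study gives up any claim about a best point. Few points may qualify for an interval: at 60 episodes and 40% use a point has about 60 × 0.4 = 24 uses, and if points are fixed within subject at 40% use, about 30 × 0.4 = 12 subjects contribute whatever the number of episodes. Intervals will be wide: at 30 episodes and a 40% rate, 1.96 × √(0.24/30) = 0.175, about ±18 points before clustering. With about 15 subjects the bootstrap still covers slightly under 95%, about 93% at an assumed ICC of 0.3.
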